7.4 Pharmacokinetics / pharmacodynamics – amended

Old text:

Profile day (Visit 1 and Visit 12)

- ~~4~~– 2 hours **after** administration of the morning dose of study medication
- 3 – 4 hours **after** administration of the morning dose of study medication

Visits 2 through to 6 and Visits 13 through to 17

- Up to 1 hour **before** administration of morning dose of study medication (trough)

Visit 11

- Up to 1 hour **before** administration of morning dose of study medication (trough)
- 2 –~~3~~ hours **after** administration of morning dose of study medication (peak)

New text:

Profile day (Visit 1 and Visit 12)

- 2 hours **after** administration of the morning dose of study medication

- 3 – 4 hours **after** administration of the morning dose of study medication

Visits 2 through to 6 and Visits 13 through to 17

- Up to 1 hour **before** administration of morning dose of study medication (trough)

Visit 11

- Up to 1 hour **before** administration of morning dose of study medication (trough)
- 2 hours **after** administration of morning dose of study medication (peak)

7.6.5 Blood pressure and heart rate measurement

New text was added in the end of the section.

New text:

Assessment of orthostatic changes

To assess orthostatic changes, blood pressure and heart rate will be measured with the patient in a supine position, after the patient has rested for 5 minutes. Immediately thereafter, the patient should sit up and blood pressure and heart rate will be measured after the patient has rested for 2 minutes.

These measurements should be performed approximately 2 hours after study medication intake.

Frequency: Visit 11 (Week 39), Visit 12 (Week 52), during the dose-titration period of the long-term extension phase (Visits 13 to 17).

7.6.18 Oxygen saturation measurement using forehead pulse oximetry

Section was newly inserted with Amendment 6.

New text:

Oxygen saturation measurements will be performed in all subjects using non-invasive forehead pulse oximetry expressing the SpO₂ (peripheral oxygen saturation) percentage. At visits with blood pressure measurements to assess orthostatic changes, oxygen saturation will be measured pre-dose and post-dose (see Table 7–2, Table 7–3, and Table 7–4). At all other visits, oxygen saturation will be measured pre-dose only.

If the patient receives supplemental oxygen, the amount [L/min] will be recorded in the eCRF.

Frequency: Visit 9 (Week 20), Visit 10 (Week 26), Visit 11 (Week 39), Visit 12 (Week 52), Visits 13 to 17 (Week 54 to 62), Visit 18 to Visit n (Open-label Extension Period), Termination Visit, and 30-day Safety Follow-up.

8.4.3 Safety

Old text:

[...]

Descriptive analysis of vital and their changes from baseline will be performed by treatment group and visit.

New text:

[...]

Descriptive analysis of vital signs and their changes from baseline will be performed by treatment group and visit. Descriptive statistics of pulse oximetry and blood pressure/heart rate measurements for the assessment of orthostatic changes will be performed by treatment group and visit.

13.5 Amendment 7

Amendment 7 is presented using a different approach to the previous amendments of this protocol. The rationale for changes in this amendment and all affected sections are provided in the “Protocol Amendment Summary of Changes Table” at the beginning of this document directly before the Table of Contents. The old/new text section detailing the changes compared to the last global CSP version has been replaced with a document edited in track change mode showing all changes, this document is available on request.

14. Appendices

14.1 Child-Pugh Classification of Liver Disease

Factor	+1	+2	+3
Bilirubin (mg/dL)	< 2	2 – 3	> 3
Albumin (g/dL)	> 3.5	2.8 – 3.5	< 2.8
International Normalized Ratio	< 1.7	1.7 – 2.3	> 2.3
Ascites	None	Mild	Moderate / Severe
Encephalopathy	None	Grade I – II or medically controlled	Grade III – IV or poorly controlled

Child-Pugh Class	A	B	C
Points	5 – 6	7 – 9	10 – 15

Source: Pugh RN, Murray-Lyon IM, Dawson JL, Pietroni MC, Williams R. Transection of the oesophagus for bleeding oesophageal varices. Br J Surg 1973;60:646-649.[38]

14.2 Definition of Systemic Sclerosis Renal Crisis - amended

Scleroderma renal crisis is defined as the new onset of severe hypertension associated with a rapid increase in serum creatinine concentration, microangiopathic hemolytic anemia, or both [39]¹⁵⁵. Systemic sclerosis renal crisis usually manifests with acute onset of moderate-to-severe ‘accelerated’ hypertension and oliguric renal failure [40].

The definition of systemic sclerosis hypertensive renal crisis is independent of whether or not concomitant antihypertensive medications are used.

History of new-onset hypertension, based on any of the following (measurements repeated and confirmed at least 2 hours apart within 3 days of first event-associated observation, with a change from baseline*). As a reminder, renal crisis is defined as meeting the first 4 signs:

1. Systolic blood pressure (SBP) \geq 140 mmHg
2. Diastolic blood pressure (DBP) \geq 90 mmHg
3. Rise in SBP \geq 30 mmHg compared to baseline
4. Rise in DBP \geq 20 mmHg compared to baseline

**Historical baseline blood pressure of the patient*

AND

At least 1 of the following 5 features:

1. Serum Creatinine: increase of \geq 50% above baseline*
2. Proteinuria: \geq 2+ by dipstick confirmed by protein: creatinine ratio $>$ ULN
3. Hematuria: \geq 2+ by dipstick or $>$ 10 RBCs/High Power Field (HPF) (without menstruation)
4. Thrombocytopenia: $<$ 100,000 platelets/mm³
5. Hemolysis: by blood smear or increased reticulocyte count

**Historical baseline creatinine of the patient*

¹⁵⁵ References 39 and 40 added per Amendment 1

14.3 Tender and Swollen Joint Count Assessment Form

TENDER & SWOLLEN JOINT COUNT ASSESSMENTS				
	Left		Right	
	Swollen	Tender	Swollen	Tender
Shoulder				
Elbow				
Wrist				
MCP 1				
2				
3				
4				
5				
PIP 1				
2				
3				
4				
5				
Knee				
Subtotal				
TOTAL	Swollen 		Tender 	
0 = Absent 1 = Present 9 = Replaced/N.A.* *Injected joints will not be assessed for a period of one month (30 days) and will be documented as "Replaced/N.A."

Systemic sclerosis (SSc) is a rare, orphan disease featuring chronic, fibrosing, autoimmune responses characterized by small vessel vasculopathy, autoantibody production, and fibroblast dysfunction leading to increased deposition of extracellular matrix. Systemic sclerosis is further divided into 2 subtypes defined by the extent of skin involvement: limited cutaneous systemic sclerosis (lcSSc) and diffuse cutaneous systemic sclerosis (dcSSc).

Both dcSSc and lcSSc are associated with internal organ involvement; however, patients with dcSSc are at greater risk for clinically significant major organ dysfunction. Diffuse cutaneous SSc is one of the most fatal rheumatic diseases, and is associated with substantial morbidity and many detrimental effects on health-related quality of life (HRQoL).

Currently, no therapy has been proven to reverse the vascular and fibrotic damage in patients with scleroderma. However, due to the high medical need, a number of drugs, such as methotrexate, mycophenolate mofetil, cyclophosphamide, azathioprine, and cyclosporine, are used off-label in an attempt to slow the progression of fibrosis. Current treatment options only target various SSc-related symptoms. No disease-modifying drug is available for SSc. In the European Union (EU), only bosentan is approved “to reduce the number of new digital ulcers in patients with SSc and ongoing digital ulcer disease” thus addressing also only one aspect of the disease.

Based on the positive results of riociguat in patients with PAH and chronic thromboembolic pulmonary hypertension (CTEPH) together with the compound’s known anti-proliferative and antifibrotic effects as seen in vitro and in animal models, patients with SSc may benefit from treatment with riociguat. The current study will be the first study testing riociguat in this indication. The efficacy and safety of riociguat in patients with dcSSc will be evaluated.

This Statistical Analysis Plan is based on the following document(s):

Integrated Clinical Study Protocol, Amendment 7, version 6.0 dated 17 APR 2018

The SAP for the main treatment phase of the study was finalized prior to unblinding to describe the evaluation the efficacy and safety of 52-week treatment (plus 30-day safety follow-up, when applicable) with riociguat compared to the placebo ([16277 Statistical Analysis Plan - Final Version 4_0](#)). The SAP describing the interim benefit-risk evaluation for the long term extension (LTE) phase was finalized on 12 JUL 2018 ([16277 Statistical Analysis Plan for Benefit-risk update version 1.0](#)). This SAP describes the complete evaluation of the LTE phase. Results from the final LTE analyses will be presented in the Addendum to the Clinical Study Report (CSR).

2. Study Objectives

The overall objective of the main phase of study 16277 was to evaluate the efficacy and safety of 52 weeks of treatment with riociguat versus placebo in subjects with dcSSc. For details on the primary and secondary objectives of the study, see the SAP of the main treatment phase.

The main focus of the evaluation of the LTE phase described in this SAP was to allow a continued exploratory assessment of benefit risk profile of riociguat.

3. Study Design

3.1 Design overview – Long term extension phase

The study design consists of a main study treatment phase followed by a LTE phase. At Visit 12 (Week 52), patients randomized to the placebo arm in the main treatment phase were initiated active treatment with riociguat, as part of the LTE phase. During the first 10 weeks, a titration/sham-titration was performed to maintain the study blind, after which the extension phase becomes open-label. During the LTE phase, clinical outcomes were continued to be measured for exploratory long-term treatment effects. Adverse event (AE) information was continued to be collected throughout the LTE phase.

As defined in the [protocol Section 4.1.3](#), the LTE phase was planned to continue up to 6 years after the last patient last visit (LPLV) in the main treatment phase. However, this study was terminated (LPLV planned in MAR 2019), following the Sponsor’s decision to stop pursuing the development of riociguat in dcSSc indication.

[figure not shown]
3.1.1 Dose-Titration period (Visits 12 to 17; Week 52 to 62)

At Visit 12 (Week 52), all patients were assigned in IxRS to treatment with riociguat. To maintain the study blinding, neither the patients prior treatment assignment nor dose were unblinded. During the first 10 weeks of LTE phase, patients previously on placebo were up-titrated on riociguat according to the dose titration algorithm described below (Section 3.1.2). Patients randomized to riociguat in the main treatment phase underwent sham titration to maintain the blinding during this period.

3.1.2 Open-label Extension period (Visit 18; Week 64 onward)

After completing the double-blind dose-titration period, from Week 64 onwards the study was open-label and the investigator and the patient were able to see the current treatment dose. All patients returned to the clinic for visits every 3 months \pm 2 weeks. Ongoing titration of riociguat within the range of 0.5 mg to 2.5mg TID remained at the discretion of the investigator, and dose reductions for safety reasons were allowed.

Figure 3–1 - LTE phase design

Dose Interruptions

Although not intended, patients could interrupt their intake of study medication for various reasons (e.g., hospitalization in a remote hospital without study medication access, safety reasons or side effects). If treatment was interrupted, the following rules were applied:

LTE phase:

- ≤ 3 consecutive days without treatment (9 missing doses) in the dose-titration period: restart at the same dose
- > 3 days but ≤ 14 consecutive days without treatment in the dose-titration period: treatment can be restarted at the discretion of the investigator at 0.5 mg TID lower than the last dose
- > 14 consecutive days without treatment in the dose-titration period: discontinue the patient from study medication.
- Interruptions in the open-label extension period:
 - > 13 and ≤ 28 consecutive days: treatment can be restarted at the discretion of the investigator at 0.5 mg TID lower than the last dose.
 - > 28 consecutive days: discontinue the patient from study medication.

3.1.3 Termination visit and Safety follow-up visit

A termination visit should have been performed for patients who discontinued, per clinical study protocol, from study medication for any reason except death or lost to follow-up, and should have occurred as soon as possible after the patient received his/her last dose of study drug. In general, at the Termination Visit the same safety and efficacy relevant measurements and procedures should have been performed as at Visit 12. If the Termination Visit was performed after Visit 12 (Week 52) the patient's and physician's global assessment, patient interference with skin assessment, and tender and swollen joint count assessment must not have been performed.

A safety follow-up visit (30 [+5] days after the last dose of study medication) were to be performed for all the patients.

3.1.4 Definition of rescue therapy

During the LTE phase (ie, after completion of all efficacy- and safety-related procedures at Visit 12), except for the contraindicated nitrates or NO donors and PDE5 inhibitors, the addition of any other concomitant medication was at the discretion of the investigator.

Use of rescue therapy agents (4 agents: methotrexate, mycophenolate mofetil, cyclophosphamide or azathioprine are counted as defined in the main SAP) will be tabulated by therapy from Week 52 to the end of the study date and overall by timepoint.

3.2 End of study

For each participating EU country, the end of the study according to the EU Clinical Trial Directive will be reached when the last visit of the last subject for all centers in the respective country has occurred.

The end of the study as a whole will be reached as soon as the end of the study according to the above definition has been reached in all participating countries (EU and non-EU).

4. General Statistical Considerations

4.1 General Principles

The statistical evaluation will be performed by using the software package SAS release 9.2 or higher (SAS Institute Inc., Cary, NC, USA).

The statistical analysis will conform to Bayer Global Standard Tables version 3.0, 16 JAN 2017 with any riociguat project-specific options for these tables, and also any additional riociguat project-specific tables (Riociguat Standard Tables version 2.0, 19 JUN 2013). Subject data listings will conform to Bayer Global Standard Listings version 3.1, 16 JAN 2017. Additional data summaries not contained within these standards will be study specific.

All variables will be analyzed by descriptive statistical methods. The number of data available and missing data, mean, standard deviation, minimum, median, quartiles (if data are clearly non-normal) and maximum will be calculated for continuous data. Frequency tables will be generated for categorical data.

All the analyses will be performed in patients valid for the full analysis set (FAS), who took part in the LTE. This is the long-term safety analysis set.

4.2 Handling of Dropouts

The frequency of enrolled subjects not completing LTE phase and associated reasons will be summarized.

A patient who discontinues study participation prematurely for any reason is defined as a “dropout”, if the patient has already been entered to LTE phase.

Any patient, if entered to long-term extension phase, removed from the trial should undergo the assessments at the termination visit.

4.3 Handling of Missing Data

All missing or partial data will be presented in the subject data listing as they are recorded on the Case Report Form (CRF).

Kaplan-Meier plot for “Time to end of study treatment” will be provided.

General rules

When appropriate, the following rules will be implemented so as not to exclude subjects from descriptive analyses due to missing or incomplete data:

- **Safety Variables**

When only partial dates are available, the following rules will be used for the derivation:

If either the day or month of the start date of the adverse event is missing, then a worst case assumption is made for the treatment-emergent flag. For example, if study medication starts on 15 JAN 2016 and the AE start date is recorded as JAN 2016, then

this is considered treatment-emergent, as it is possible the adverse event started while the patient is on study medication.

4.4 Interim Analyses and Data Monitoring

No formal interim analyses for LTE phase will be done. There will be no Data Monitoring Committees either.

4.5 Data Rules

Analysis datasets (ADS) containing all derived variables needed for the statistical evaluation will be generated. The structure of the ADS and the contained variables will be described in a separate specification document.

Efficacy analysis datasets will be created that include key data, such as demography, flag for use of rescue medication, baseline efficacy. Relative days and flags for treatment emergent events are included in the databases.

The rules for data handling are described in detail in the Project Data Handling Rules, current version 1.2, dated 09 JAN 2014, and any updated versions becoming available during the course of this study.

4.5.1 Definition of baseline and handling of repeated measurements

Baseline for the main phase is defined as the last set of non-missing measurements taken prior to the first intake of study medication, called ‘baseline for main treatment phase’.

In case of multiple measurements per post baseline visit, the last non-missing value per visit will be taken for analysis.

For LTE phase, Week 52 will serve as baseline measurement for LTE (‘baseline for LTE phase’) to be compared with measurements during the LTE phase.

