- w Oxygen saturation will be measured using forehead pulse oximetry. At visits with blood samples for PK and blood pressure measurements for the assessment of orthostatic changes, post-dose measurements will be performed in addition to pre-dose measurements (see Section 7.6.18, Table 7-2, Table 7-3, Table 7-4)⁷⁰
- x Measure supine and sitting blood pressure and heart rate to check for orthostatic changes approximately 2 hours after intake of study medication. (see Section 7.6.5, Table 7-2, Table 7-3, Table 7-4).⁷¹

⁶⁷ Per Amendment 4

⁶⁸ Per Amendment 1

⁶⁹ Per Amendment 4

⁷⁰ Per Amendment 6

⁷¹ Per Amendment 6

Pharmacokinetics sampling flow charts - amended

Profile day (Visit 1 and Visit 12)

- 2 hours **after** administration of the morning dose of study medication⁷²
- 3 – 4 hours **after** administration of the morning dose of study medication

Table 7–2 Profile Day PK Sampling (Visit 1 and Visit 12)⁷³

Visit 1 and Visit 12 (profile days)			Cycle of procedures				
Order of procedures	Starting point of procedures	Time interval (h)	00	00	1:45 – 2 h	2h	3 – 4 h
			↓	At Visit 12 only: oxygen saturation using forehead pulse oximetry	X		
	Blood pressure, heart rate	X					
	Administration of morning dose of study medication			X			
	At Visit 12 only: oxygen saturation using forehead pulse oximetry				X ^a		
	Blood pressure, heart rate; at Visit 12 only: supine and sitting position				X ^a		
	Blood sample for PK					X	
	Blood pressure, heart rate (within 20 minutes prior to PK sample)						X
	Blood sample for PK						X

^a At Visit 12 only: measure oxygen saturation, blood pressure and heart rate in supine and sitting position (see Section 7.6.5 and Section 7.6.18).

Abbreviations: h = hours; PK = pharmacokinetic.

Visits 2 to 6 and Visits 13 to 17

- Up to 1 hour **before** administration of the morning dose of study medication (trough)

Table 7–3 PK Sampling (Visits 2 – 6 and Visits 13 – 17)⁷⁴

Visit 2 to Visit 6 and Visit 13 to Visit 17			Cycle of procedures			
Order of procedures	Starting point of procedures	Time interval (h)	-1 h – 00	00	00	2h
			↓	Blood sample for PK	X	
	Visit 13-17 only: oxygen saturation using forehead pulse oximetry			X		
	Blood pressure, heart rate			X		
	Administration of morning dose of study medication				X	
	Visit 13-17 only: oxygen saturation using forehead pulse oximetry					X
	Visits 13-17 only: Blood pressure, heart rate in supine and sitting position					X

⁷² Per Amendment 6

⁷³ Per Amendment 6

⁷⁴ Per Amendment 6

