- Vital signs (blood pressure and heart rate) should be measured within 20 minutes prior to each PK sampling with the patient in a sitting position and after the patient has been at rest for at least 5 minutes. The same arm is always used for these measurements (see Section 7.6.5).

⁸⁰ Per Amendment 6

⁸¹ Per Amendment 6

7.1.2.6 Visits 13 through to 17 – Long-term extension phase - Dose-titration period - amended

At these study visits, the patient should attend the clinic without having taken the morning dose of riociguat.

During the double-blind dose-titration period of the long-term extension phase, the following assessments will be performed according to the Schedule of evaluations (Section 7.1.1):

- Oxygen saturation will be measured before and after intake of study drug (see Section 7.6.18, Table 7–2, Table 7–3, and Table 7–4)⁸²
- Vital signs (blood pressure and heart rate). Blood pressure and heart rate will be measured at all visits with the patient in a sitting position, after the patient has been at rest for at least 5 minutes. The same arm is always used for these measurements (see Section 7.6.5)
- Assessment of orthostatic changes: measure blood pressure and heart rate in supine position and sitting position approximately 2 h after intake of study drug (see Section 7.6.5).⁸³
- Digital ulcer net burden assessment (see Section 7.6.10)
- Blood samples for safety (Visit 17; see Section 7.6.2)
- Blood sample for PK up to 1 hour before the morning dose of study drug (see Section 7.4)
- Pregnancy test (urine) for all women of childbearing potential (on-site at Visits 14 and 16) (see Section 7.6.1)
- Recording and assessment of AEs (see Section 7.5)
- Concomitant therapy
- Dose titration according to the titration algorithm (see Section 4.1.2)
- Dispensation of study drug and drug accountability

7.1.2.7 Visits 18 through Visit n (every 12 weeks) – Long-term extension phase – Open-label extension period - amended

At these study visits, the patient should attend the clinic without having taken the morning dose of riociguat.

During the open-label extension period, the following assessments and procedures will be performed according to the Schedule of evaluations (Section 7.1.1):

- Questionnaires (see Section 7.6.13)
- Smoking history
- Physical examination, including weight

⁸² Per Amendment 6

⁸³ Per Amendment 6

- Oxygen saturation measurement using forehead pulse oximetry (see Section 7.6.18).⁸⁴

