7.6.18 Oxygen saturation measurement using forehead pulse oximetry¹¹⁹

Oxygen saturation measurements will be performed in all subjects using non-invasive forehead pulse oximetry expressing the SpO₂ (peripheral oxygen saturation) percentage. At visits with blood pressure measurements to assess orthostatic changes, oxygen saturation will be measured pre-dose and post-dose (see [Table 7-2](#), [Table 7-3](#), and [Table 7-4](#)). At all other visits, oxygen saturation will be measured pre-dose only.

If the patient receives supplemental oxygen, the amount [L/min] will be recorded in the eCRF.

Frequency: Visit 9 (Week 20), Visit 10 (Week 26), Visit 11 (Week 39), Visit 12 (Week 52), Visits 13 to 17 (Week 54 to 62), Visit 18 to Visit n (Open-label Extension Period), Termination Visit, and 30-day Safety Follow-up.

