13.4.1 Overview of changes to the study

This amendment was implemented based on the recommendation of the data monitoring committee (DMC) after review of the safety analysis on 01 MAR 2017. Due to increased complaints of both palpitations and dizziness in subjects with interstitial lung disease (ILD) noted by the DMC, the assessment of orthostatic changes in blood pressure and heart rate as well as the measurement of oxygen saturation (using forehead pulse oximetry) were added to the protocol assessments for all subjects. As recruitment for this study was already completed, the new assessments will not be implemented starting with the screening visit, but only for study visits, which will be performed after implementation of this amendment.

Additionally, an error in the description of the units provided in exclusion criterion 6 was corrected.

Correction of typographical errors and minor editorial changes are not specified in the list of changes below. New text is displayed as underlined; text that was deleted is presented as strike-through text.

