6.4.3 Other safety parameters

Descriptive analysis of weight and vital signs, pulse oximetry and their changes from Week 52 (which is the baseline for the LTE analysis) until end of the study will be performed.

Number of subjects with low/normal/high vital signs, will be tabulated by treatment group and

visit. Assessments for orthostatic test will be listed. The number of subjects with abnormal ECG findings, as well as the number of subjects with treatment-emergent ECG abnormalities will be tabulated by treatment group from Week 52 to the end of the study.

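### As written, the SAP's last-value rule mixes post-dose and pre-dose oxygen saturation across extension visits, and orthostatic data that the protocol says will be summarised are only listed

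*SAP*

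**What the plan says.** **Oxygen saturation.** SAP 6.4.3 plans a "Descriptive analysis of weight and vital signs, pulse oximetry and their changes from Week 52" until the end of the study. For several values at one visit, SAP 4.5.1 states: "In case of multiple measurements per post baseline visit, the last non-missing value per visit will be taken for analysis". Neither section separates values taken before a dose from values taken after it. SAP 4.5.1 makes Week 52 the extension baseline without saying on which side of the Visit 12 dose it falls. It writes a before-first-intake condition only for the main phase.

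The protocol does make the distinction. For visits with PK sampling and orthostatic measurements, Table 7-1 footnote w says "post-dose measurements will be performed in addition to pre-dose measurements". The Visit 12 list (7.1.2.5) says "Oxygen saturation will be measured before and after intake of study drug", and 7.1.2.6 says the same for Visits 13 to 17. Table 7-3 places the second reading at 2 h. Protocol 7.6.18 adds: "At all other visits, oxygen saturation will be measured pre-dose only". That covers Visit 18 onward.

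**Orthostatic measurements.** Protocol 8.4.3 plans descriptive statistics of the orthostatic blood pressure and heart rate measurements, by treatment group and visit. SAP 6.4.3 provides a listing. SAP section 7, whose title covers changes in the planned analysis, names two earlier SAP approvals and does not mention this difference.

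**The concern.** A table of change from Week 52 is readable across visits only if each visit's value is taken under the same conditions. Here the timing relative to the dose would switch between Visit 17 and Visit 18. A reader could not separate a change over time from a change in when the reading was taken. Visits 13 to 17 are also the visits at which former placebo patients are titrated on riociguat.

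Both sets of measurements have a safety origin. Amendment 6 added "the assessment of orthostatic changes in blood pressure and heart rate as well as the measurement of oxygen saturation" on the data monitoring committee's recommendation, after increased complaints of palpitations and dizziness in patients with interstitial lung disease. For the extension, SAP 4.4 says: "There will be no Data Monitoring Committees either". The extension report is thus a main place where these data would be seen in aggregate. A listing gives no picture by group and visit.

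**Working it through.** The plan states no figure to reproduce. The check applies the SAP rule to the protocol's schedule.

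**Step 1: value selected at each visit** (protocol 7.6.5, 7.6.18, Tables 7-2 and 7-3)

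| Visit | Planned saturation readings | Last reading |
|---|---|---|
| 12 (extension baseline visit) | pre-dose, post-dose | post-dose |
| 13 to 17 | pre-dose, 2 h post-dose | post-dose (5 of 5 visits) |
| 18 onward | pre-dose | pre-dose |

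The Visit 12 post-dose reading follows the first extension dose, so in former placebo patients it is already taken on riociguat. Table 7-1 footnote a calls Visit 12 the extension's baseline visit, which favours a pre-dose baseline. The last-value rule favours post-dose if Visit 12 is handled as a post-baseline visit of the main phase.

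**Step 2: effect when nothing truly changes.** Let d = post-dose minus pre-dose saturation, and m = share of patients whose post-dose value is missing at Visits 13 to 17, for whom the rule falls back to pre-dose. Neither is in the documents. Assumed here: d from -2 to +1 points, m of 0 or 20%.

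- Pre-dose baseline: mean change is (1 - m)d at Visits 13 to 17 and 0 from Visit 18.
- Post-dose baseline: mean change is -md at Visits 13 to 17 and -d from Visit 18.
- Step from Visit 17 to Visit 18, either baseline: -(1 - m)d.

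| d | Step, m = 0 | Step, m = 20% |
|---|---|---|
| -2 | +2 | +1.6 |
| -1 | +1 | +0.8 |
| -0.5 | +0.5 | +0.4 |
| +0.5 | -0.5 | -0.4 |
| +1 | -1 | -0.8 |

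The choice of baseline moves the artefact from one set of visits to the other but does not remove the step. If one dose timing is used at Week 52 and at every visit compared with it, the shift is 0 for any d and m.

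**Step 3: availability of a Week 52 value.** Amendment 6 was approved on 02 May 2017 and applies the new assessments "but only for study visits, which will be performed after implementation of this amendment". Visit 12 is Day 364, and 02 May 2017 minus 364 days is 03 May 2016. By nominal days, patients randomised before that date had Visit 12 before approval and so no Week 52 saturation. Visit 17 is Day 434, and 02 May 2017 minus 434 days is 23 Feb 2016. Patients randomised before then were also past Visit 17. Visit windows and later local implementation move these dates later. The documents give no randomisation dates, so the number affected is unknown and could be zero.

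**Step 4: orthostatic data.** Protocol 7.6.5 plans the test at Visits 11, 12 and 13 to 17, seven visits in all. Five of these fall in the period this SAP covers. For those five, the protocol says statistics by group and visit and the SAP says a listing.

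**The case against.** - **The rule may be meant only for duplicates.** Its section concerns repeated measurements, and pre-dose and post-dose readings are two planned assessments. SAP 6.3 computes drug-concentration statistics for each sampling point, and SAP 6.4.3 names the orthostatic test separately from vital signs. The intended reading may therefore be separate time points, in which case the step vanishes. But SAP 6.3 also shows that the SAP can say so when it means it, and for oximetry it does not.
- **Other documents may settle it.** SAP 4.5 refers to project data-handling rules, including later versions, and to a dataset specification. Neither was available. The cited version 1.2 (January 2014) predates oximetry in this trial, though an update could cover it.
- **A reader might infer that the table would show a false titration effect.** The documents do not support going that far. SAP section 6 shows Riociguat-Riociguat beside Placebo-Riociguat, both on the same measurement schedule, with sham titration in the former. A timing artefact would tend to appear in both groups, and a titration effect mainly in one. The protection is incomplete, since the SAP itself warns that the groups may not be comparable.
- **A reader might infer that the orthostatic data are summarised nowhere.** That cannot be said. The main-phase SAP may cover Visits 11 and 12. The benefit-risk SAP of 12 July 2018 may cover Visits 13 to 17: main-phase results existed by Amendment 7 (17 April 2018), and Visit 17 is nominally 70 days (434 - 364) after Visit 12, so those visits were due by about 26 June 2018. Still, the present SAP calls itself the complete evaluation of the extension and cites no such summary. The general sentence in SAP 4.1 that all variables are analysed descriptively does not replace the specific plan for a listing.
- **A reader might infer that patient monitoring was weakened.** This SAP was written after the sponsor stopped development in this indication. Table layout now affects interpretation, not monitoring during titration.

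**Conclusion.** Both parts hold, as minor points.

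1. SAP 4.5.1 as written gives a saturation series that is post-dose at Visits 13 to 17 and pre-dose from Visit 18, with the dose timing of the Week 52 baseline undefined. Change from Week 52 therefore mixes dose timings across visits. This rests on applying the SAP text literally. The size and sign are not in the documents: 0.5 to 2 points is an assumption for a post-dose fall, the sign reverses if saturation rises after the dose, and the artefact is zero if time points are in fact summarised separately.
2. The mismatch between protocol 8.4.3 and SAP 6.4.3 on orthostatic data needs no assumption. What remains unknown is whether another SAP already supplied the summary.

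No test, significance level or power is affected. The outputs are descriptive, SAP section 6 calls all results exploratory, and absolute values are shown beside changes.

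**What to change.** 1. Summarise pre-dose and post-dose oxygen saturation separately by visit, each against the Week 52 value with the same dose timing. Define the extension baseline for vital signs, and for the pre-dose saturation comparison, as the last value before the first extension dose. If the data-handling rules or dataset specification already do this, cite them in SAP 4.5.1.
2. Use the available and missing counts that SAP 4.1 already requires to show how many patients lack a matched Week 52 saturation value.
3. Tabulate the orthostatic blood pressure and heart rate measurements at Visits 13 to 17 by group and visit, as protocol 8.4.3 states, or cite the SAP in which they were already summarised.

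The cost is SAP wording, programming and a few more tables, with no new data collection. The downside is that fewer patients will have a matched Week 52 saturation value, because oximetry began only with Amendment 6.
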